6.1.2. Primary Analysis of the Primary Efficacy Endpoint

The primary comparison will be made using an analysis of covariance (ANCOVA) model, including baseline value, stratification factors, and treatment group. The estimated least square means of treatment effects and estimated difference in treatment effects between treatment groups at Week 24 will be presented along with the 95% CIs and p-values. The primary analysis will be based on observed data.

Summary statistics (sample size, mean, SD, median, Q1, Q3, minimum, and maximum) will be provided for the observed and change from Baseline by treatment group and study visit.

Analysis will be based on observed data only. No imputation will be done for missing data.

6.2. Changes From Protocol-Specified Efficacy Analyses

Since the study is terminated early, the analyses for the key secondary and other secondary endpoints specified in the protocol are not performed.

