10.4.2 Analysis of Secondary and Exploratory Endpoints

Secondary and exploratory endpoints will be analyzed descriptively. All secondary and exploratory endpoints will be summarized ([Section 3.2.2](#) and [Section 3.2.3](#)).

For continuous variables, such as observed and change from Baseline HBV DNA values at each timepoint, descriptive statistics will be used, and will include the number, mean, standard deviation, median, minimum, maximum, and, where appropriate, a 95% confidence interval. Missing data methods and imputation rules will be defined in the SAP. Additional sensitivity analysis may also be performed and will be described in the study SAP.

For categorical variables, such as subjects with a reduction in HBV DNA below LLOQ, descriptive statistics will include number and percent who meet the endpoint criterion.

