1. INTRODUCTION

Study ABI-H2158-201 is a Phase 2a, multicenter, randomized, single-blind, placebo (PBO)-controlled, multiple cohort study evaluating ABI-H2158-containing regimens in chronic hepatitis B virus (HBV) infection (cHBV). The target population is male or female subjects with cHBV, 18 to 65 years of age, inclusive, with no evidence of cirrhosis or end-stage liver disease. Cohort 1 will enroll treatment-naïve subjects with hepatitis B virus “e” antigen (HBeAg) positive cHBV. Cohort 2 will enroll treatment-naïve subjects with HBeAg negative cHBV.

This statistical analysis plan (SAP) describes the statistical analysis methods and data presentations to be used in tables, figures, and listings (TFLs) in the clinical study report (CSR) for Study ABI-H2158-201. This SAP is based on the Study Protocol Amendment 2, dated 14 December 2020; UK country-specific protocol amendment, dated 17 December 2020; Korea-country specific protocol amendment, dated 05 February 2021; ABI-H2158-201 Protocol Clarification Letter for Amendment 2; dated 14 Dec 2020, 07 September 2021; and the electronic case report form (eCRF). On 01 September 2021, Assembly made the decision to discontinue the development of ABI-H2158 following the observation of elevated alanine aminotransferase (ALT) levels consistent with drug-induced liver injury (DILI) in study ABI-H2158-201. Therefore, only key safety and efficacy endpoints will be performed. The SAP will be finalized before final database lock. Any changes made after the finalization of the SAP will be documented in the Synoptic CSR.

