1.1. Study Objectives

The primary objectives of this study are as follows:

- To evaluate the safety and tolerability of ABI-H2158 when administered in combination with entecavir (ETV) in subjects with cHBV
- To evaluate the effect of ABI-H2158 in reducing HBV DNA in subjects with cHBV

The secondary objectives of this study are as follows:

- To evaluate the pharmacokinetics (PK) of ABI-H2158 and ETV in subjects with cHBV
- To evaluate the effect of ABI-H2158 in reducing HBV pregenomic RNA (pgRNA) levels in subjects with cHBV
- To evaluate the effect of ABI-H2158 in reducing HBV antigens (ie, HBeAg, hepatitis B core-related antigen [HBcrAg] and hepatitis B surface antigen [HBsAg]) in subjects with cHBV
- To evaluate the effect of ABI-H2158 on normalization of ALT in subjects with abnormal ALT
- To evaluate the emergence of resistance to ABI-H2158 when administered in combination with ETV

The exploratory objectives of this study are as follows:

- To assess the relationship between new and known viral biomarkers and virologic and/or clinical outcomes
- For subjects who provide an optional pharmacogenomic sample, to evaluate the potential contribution of host genomics to clinical or virologic outcomes and/or drug disposition

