1.3. Sample Size and Power

It is planned that approximately 80 subjects (40 subjects per Cohort 1 and Cohort 2) will be enrolled in this study. Subjects will be randomized to receive either 300 mg ABI-H2158 or PBO or in a 3:1 ratio. That is, 30 subjects randomized to treatment with ABI-H2158 per Cohort 1 and Cohort 2 and 10 subjects will be randomized to treatment with PBO per Cohort 1 and 2. This sample size is not based on statistical considerations but is considered adequate for a proof-of-concept study.

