2. TYPE OF PLANNED ANALYSIS

2.1. DRC Interim Analyses

An internal DRC will perform regular unblinded reviews of safety data to ensure timely analysis of any emergent safety/tolerability issues, and completion of the prespecified safety data reviews. As this is an exploratory Phase 2a study, the DRC will also assess the unblinded HBV virology parameter (HBeAg, HBsAg, HBcrAg, HBV DNA and HBV pgRNA) results at prespecified timepoints before the final analysis to make strategic decisions relating to drug development. The aggregated virology data may be released for external communication.

The initial DRC review will be conducted after approximately 25% of planned enrolled subjects in Cohort 1 have completed at least 4 weeks of treatment. Additional meetings will be scheduled approximately every month. In addition to regular review of safety and virology data, the DRC will also review the interim PK analysis when all randomized subjects in each cohort or approximately 2-5 subjects from South Korean sites, have completed Week 4 assessments or discontinued before completing Week 4.

The DRC will comprise Sponsor's representatives from Clinical Research and Biometrics. Other functional area members may be included as necessary. The DRC's role and responsibilities and the scope of the analysis will be provided in a charter, which will define the DRC membership, meeting logistics, and meeting frequency. The DRC members will not be directly involved in the study conduct and will not have interactions with the study sites. The unblinded study results they may review and the meeting minutes, along with any decisions or recommendations made, will be archived in a secure location. All other Sponsor personnel will remain blinded until completion of the study.

The study remains blinded following the study termination. The DRC meetings are held to review and monitor the safety data after study drug discontinuation before the study unblinding.

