3.6.2. Analysis Visit Windows

Subject visits might not occur on protocol-specified days. Therefore, for the purpose of analysis, observations will be assigned to analysis windows. In general, the baseline value will be the last nonmissing value on or prior to the first dose date of study drug. The “on-treatment” period is defined up to the last dose date of ABI-H2158/PBO. The “off-treatment” period is defined after the last dose of ABI-H2158/PBO through the follow up period.

The assessment schedule is different in the Korea country specific protocol amendment. The analysis window will follow what is specified in the global protocol.

The analysis windows for on-treatment study assessments, including HBV DNA, HBV pgRNA, HBsAg, HBeAg, HBcrAg, adverse events, and clinical laboratories (chemistry, hematology, coagulation, urinalysis) are provided in [Table 3-1](#).

Table 3-1. On-Treatment Analysis Visit Windows for Study Assessments

Nominal Visit	On-Treatment Nominal Study Day	Visit Window Study Day	
		Lower Limit	Upper Limit
Day 1	1	(none)	1
Week 2	14	2	21
Week 4	28	22	42
Week 8	56	43	70
Week 12	84	71	98
Week 16	112	99	126
Week 20	140	127	154
Week 24	168	155	182
Week 28	196	183	210
Week 32	224	211	238
Week 36	252	239	266
Week 40	280	267	294
Week 44	308	295	322
Week 48	336	323	350
Week 52	364	351	378
Week 56	392	379	406
Week 60	420	407	434
Week 64	448	435	462
Week 68	476	463	490

Nominal Visit	On-Treatment Nominal Study Day	Visit Window Study Day	
		Lower Limit	Upper Limit
Week 72	504	491	≥504

The analysis windows for electrocardiograms (ECG) measurements are provided in [Table 3-2](#).

Table 3-2. On-Treatment Analysis Visit Windows for ECG

Nominal Visit	On-Treatment Nominal Study Day	Visit Window Study Day	
		Lower Limit	Upper Limit
Day 1	1	(none)	1
Week 12	84	2	126
Week 24	168	127	210
Week 36	252	211	294
Week 48	336	295	378
Week 60	420	379	462
Week 72	504	463	≥504

The analysis windows for off-treatment study assessments, including HBV DNA, HBV pgRNA, HBsAg, HBeAg, HBcrAg, vital signs, concomitant medications and adverse events, chemistry, hematology, coagulation and urinalysis are provided in [Table 3-3](#).

Table 3-3. Off-Treatment Analysis Visit Windows for Study Assessments

Nominal Visit	Off-Treatment Nominal Study Day	Visit Window Study Day	
		Lower Limit	Upper Limit
FU-Week 4	28	1	42
FU-Week 8	56	43	70
FU-Week 12	84	71	≥84

The analysis windows for ECG is provided in [Table 3-4](#).

Table 3-4. Off-Treatment Analysis Visit Windows for ECG

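### SAP 6.2 drops the secondary efficacy analyses, leaving seven of the eight protocol secondary endpoints with no final analysis in the SAP, although SAP 1.1 keeps all five secondary objectives

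*Combined protocol and SAP*

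**What the plan says.** Protocol 10.4.2 commits to a descriptive treatment of everything below the primary endpoint: "All secondary and exploratory endpoints will be summarized". Protocol 10.4.3 adds a descriptive PK analysis at Week 4 and again at the end of the study.

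The SAP was written after the decision of 01 September 2021 to discontinue the compound. Its introduction gives the reason and the consequence: "Therefore, only key safety and efficacy endpoints will be performed". SAP 6.2 then says that "the analyses for the key secondary and other secondary endpoints specified in the protocol are not performed".

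Other parts of the SAP were not adjusted to match:

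- SAP 1.1 repeats all five secondary objectives without qualification, for example "To evaluate the effect of ABI-H2158 in reducing HBV pregenomic RNA (pgRNA) levels in subjects with cHBV" and "To evaluate the effect of ABI-H2158 on normalization of ALT in subjects with abnormal ALT".
- SAP 3.6.2 still covers the dropped markers: "The analysis windows for on-treatment study assessments, including HBV DNA, HBV pgRNA, HBsAg, HBeAg, HBcrAg, adverse events". Its off-treatment windows list the same virology parameters.
- SAP 2.1 has the internal, unblinded DRC look at HBeAg, HBsAg, HBcrAg, HBV DNA and pgRNA before the final analysis, and adds: "The aggregated virology data may be released for external communication".

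**The concern.** A reader of the SAP finds secondary objectives that no specified final analysis answers, and visit windows for pgRNA and the antigens that no specified final analysis uses. Early termination is the only reason given. It does not by itself explain the choice, because the SAP keeps the more demanding analysis, a Week 24 ANCOVA of HBV DNA with confidence intervals and p-values, and drops simple summaries of markers scheduled at the same visits.

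Two things are at stake. First, the synopsis expects that deeper suppression of HBV DNA and pgRNA will lead to falls in the viral antigens. The retained analysis covers the HBV DNA part of that chain; nothing in the final plan covers pgRNA or the antigens after baseline. Second, interim pgRNA and antigen results could enter the public domain through the DRC route with no final, cleaned set of results to check them against.

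**Working it through.** The plan has no figure to reproduce here. The sample size offers none either: "This sample size is not based on statistical considerations but is considered adequate for a proof-of-concept study". The check is a comparison of Protocol 3.2.2 with the analyses that the SAP specifies for the final report.

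| Secondary endpoint (Protocol 3.2.2) | Final analysis specified in the SAP |
|---|---|
| 1. Trough levels and trough-to-peak ratios of both drugs | None. Interim DRC review only (SAP 2.1); SAP 3.1 has no PK set, though Protocol 10.3 defines one |
| 2. HBV DNA change at each timepoint | Yes: observed and change values by arm and visit (SAP 6.1.2) |
| 3. pgRNA change | None after baseline (baseline in SAP 5.2) |
| 4. HBV DNA below LLOQ | None |
| 5. pgRNA below LLOQ | None |
| 6. HBeAg, HBcrAg and HBsAg change | None after baseline (baseline in SAP 5.2) |
| 7. ALT normalisation | None. ALT appears at baseline (SAP 5.2) and as safety data (SAP 7.2) |
| 8. Variants with reduced susceptibility | None |

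Count: 8 endpoints − 1 retained = 7 without a final analysis in the SAP. The retained one serves the HBV DNA objective, which is a primary objective.

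Next, is the gap forced by the data? Protocol 7.4 and Appendix 1 schedule pgRNA at every on-treatment visit, as for HBV DNA, and the antigens at every one except Week 2. At Week 24 all are scheduled together. If the HBV DNA results at a visit are worth summarising, the other markers available at that visit can be summarised in the same way. The schedule shows planned sampling only. It does not show how many subjects reached each visit or how many samples were assayed.

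Finally, are the rules in place? SAP 3.4 covers values below LLOQ and the log10 transformation, SAP 3.6.2 gives the windows, and SAP 3.6.3 gives a record-selection rule for virology parameters. One definition is missing: SAP 5.2 groups baseline ALT by two upper limits of normal (Covance and AASLD), and nothing says which defines normalisation.

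The wording of SAP 6.2 also does not map onto the protocol. It refers to key secondary endpoints, but Protocol 3.2.2 designates none, and it is silent on the exploratory endpoints.

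**The case against.** The best defence is that the SAP is open about the reduction. It gives a dated safety reason that has nothing to do with virology, records the change under its own heading, states that the study remains blinded after termination, and is to be finalised before database lock. A synoptic report on a discontinued compound may reasonably be short. Repeating the protocol's objectives is accurate background, and a shared windows table contradicts nothing. All of this stands, and it makes the point one of scope and completeness.

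Three stronger readings are tempting, and the documents do not support them.

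- A reader might infer that every secondary analysis is gone. HBV DNA by visit survives, and SAP 6.2 is headed as a change to efficacy analyses, so it does not clearly speak to PK.
- A reader might infer that the data will go unreported. Baseline pgRNA, antigens and ALT are summarised and listed. Post-baseline ALT is analysed as safety data through graded abnormalities and the ALT elevation criteria, and the listing of graded laboratory results shows all values for the tests concerned. The general listing statement in SAP 3 neither names nor excludes virology. What is missing is a planned final summary.
- A reader might infer selective reporting, because the scope was cut in a study whose plan included unblinded looks. Only the DRC was to be unblinded, other sponsor personnel were to stay blinded, and nothing links its virology results to the cut.

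The release argument also has limits. SAP 2.1 permits release but does not record one, and the sentence covers virology only, so it does not bear on ALT normalisation or PK.

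What the defence leaves unanswered is why the HBV DNA model is kept while descriptive summaries of markers from the same visits are dropped, and which objectives the report will leave open.

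**Conclusion.** The point holds as a gap between objectives and analyses. Seven of the eight protocol secondary endpoints have no final analysis in the SAP; for PK there is an interim DRC review. Early termination alone does not account for this, given what SAP 6.1.2 retains. The gap does not affect the primary efficacy analysis or the safety analyses, and the plan as written gives no ground for alleging biased reporting.

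The conclusion assumes that the SAP is the complete plan for the final report, so that no separate PK or resistance report covers those endpoints; the documents mention none. It also assumes that some post-baseline pgRNA and antigen results exist. How many cannot be read from the documents. It is an inexpensive improvement that should be made before the SAP is final.

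**What to change.** In SAP 6.2, replace the blanket statement with the following, on available results and without testing:

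- By cohort, arm and visit, n, mean, SD, median and range of log10 pgRNA, HBsAg, HBeAg and HBcrAg, both observed and change from Baseline.
- By cohort, arm and visit, n (%) with HBV DNA below LLOQ and n (%) with pgRNA below LLOQ.
- By cohort, arm and visit, n (%) of subjects with abnormal Baseline ALT whose ALT is normal, naming which of the two upper limits (Covance or AASLD) applies.
- A line for each remaining objective (PK, resistance, exploratory) stating whether it is reported elsewhere or not addressed.
- Removal of the reference to key secondary endpoints, since the protocol has none.

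If the full set is judged too much for a synoptic report, the minimum is a final summary of every parameter that has been or will be released externally under SAP 2.1.

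The cost is a few more descriptive tables, built largely on windows and rules already in the SAP, plus one decision on the ALT limit. The tables can cover only samples that were actually assayed, so each should show its n.

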7. SAFETY ANALYSES

7.1. Adverse Events and Deaths

7.1.1. Adverse Event Dictionary

Clinical and laboratory adverse events (AEs) will be coded using the Medical Dictionary for Regulatory Activities (MedDRA) v23.0. System organ class (SOC), high-level group term (HLGT), high-level term (HLT), preferred term (PT), and lower-level term (LLT) will be provided in the AE dataset.

7.1.2. Adverse Event Severity

Adverse events are graded by the Investigator as Grade 1, 2, 3, or 4 according to the toxicity criteria specified in the protocol. The severity grade of events for which the Investigator did not record severity will be categorized as “missing” for tabular summaries and data listings. The missing category will be listed last in summary presentation.

7.1.3. Relationship of Adverse Events to Study Drug

Related AEs are those for which the Investigator selected “Related” on the AE eCRF to the question of “Relationship to Study Treatment” based on the his/her clinical assessment. Events for which the Investigator misses to record a relationship to ABI-H2158/PBO or to ETV will be considered related to the corresponding drug for summary purposes. However, by-subject data listings will show the relationship as missing.

7.1.4. Serious Adverse Events

Serious adverse events (SAEs) will be identified and captured as SAEs if the AEs met protocol-specified definitions of a SAE.

7.1.5. Treatment-Emergent Adverse Events

7.1.5.1. Definition of Treatment-Emergent Adverse Events

Treatment-emergent adverse events (TEAEs) are defined as any AEs with an onset date on or after first dose date of study drug and no later than 28 days after permanent discontinuation of ABI-H2158/PBO.

7.1.5.2. Incomplete Dates

If the onset date of the AE is incomplete and the AE stop date is not prior to the first dose date of study drug, then the month and year (or year alone if month is not recorded) of onset determine whether an AE is treatment emergent. The event is considered treatment emergent if both of the following 2 criteria are met:

- The AE onset is in the same or after the month and year (or year) of the first dose date of study drug, and
- The AE onset date is the same as or before the month and year (or year) of the date corresponding to 28 days after the date of the last dose of ABI-H2158/PBO

An AE with completely missing onset and stop dates, or with the onset date missing and a stop date later than the first dose date of study drug, will be considered to be treatment emergent. In addition, an AE with the onset date missing and incomplete stop date with the same or later month and year (or year alone if month is not recorded) as the first dose date of study drug will be considered treatment emergent.

7.1.6. Summaries of Adverse Events and Deaths

Treatment emergent AEs will be summarized based on the Safety Analysis Set.

A brief, high-level summary of the number and percentage of subjects who experienced at least 1 TEAE in the categories described below will be provided by treatment group. In addition, a table for each category showing the number and percentage of subjects will be provided by PT and treatment group in descending order of total frequency:

- TEAEs
- TEAEs by severity grade
- TE SAEs
- TEAEs leading to ABI-H2158/PBO discontinuation
- TEAEs leading to ETV discontinuation
- TEAEs leading to study discontinuation
- TEAEs related to ABI-H2158/PBO
- TEAEs related to ETV
- TE SAEs related to ABI-H2158/PBO
- TE SAEs related to ETV
- COVID-19 specific TEAEs
- COVID-19 specific TE SAEs

Multiple events will be counted only once per subject in each summary. For summary by severity grade, the most severe grade will be used for those AEs that occurred more than once in an individual subject during the study.

A brief, high-level summary of the number and percentage of subjects who experienced at least 1 off-treatment AE in the same categories as the TEAEs except for the AEs leading to ABI-H2158/PBO discontinuation will be provided by treatment group. In addition, a table for each category showing the number and percentage of subjects will be provided by PT and treatment group in descending order of total frequency. The off-treatment AEs are counted starting from 29 days after the last dose of ABI-H2158/PBO.

A data listing containing all AEs will be provided.

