All safety, antiviral activity and PK endpoints will be summarized using descriptive statistics by dose groups within cohorts. Continuous endpoints will be described using the mean, standard deviation, median, minimum, maximum. Categorical endpoints will be described using the number and percent of subjects who meet the endpoint criterion.

Due to sample size limitations, no formal statistical inference is planned. Assessment of antiviral activity will be compared by dose groups within cohorts using an appropriate 95% confidence intervals where appropriate.

Key Eligibility:

Inclusion Criteria

Subjects must meet **all** the following inclusion criteria in order to be eligible for the study:

1. Willing and able to provide informed consent
2. Male or female between the ages 18 and 65 years (inclusive)
3. Female subjects must be non-pregnant and have a negative serum pregnancy test at Screening and a negative urine pregnancy test predose on Day 1
4. Chronic hepatitis B infection, defined as HBV infection for ≥ 6 months documented, for example, by at least two measurements of HBsAg positivity and/or detectable HBV DNA ≥ 6 months apart (inclusive of Screening). For subjects without clear documentation of CHB, anti-hepatitis B core antigen immunoglobulin M (IgM) antibody to the HBV core antigen (HBcAb) must be negative at Screening to exclude acute HBV infection
5. Body mass index (BMI) 18 to 36 kg/m² and a minimum body weight of 45 kg (inclusive)
6. HBV DNA $\geq 2 \times 10^5$ IU/mL for subjects who are treatment naïve HBeAg positive
7. HBV DNA $\geq 2 \times 10^3$ IU/mL for subjects who are treatment naïve HBeAg negative

8. HBsAg >1000 IU/mL at Screening for subjects who are treatment naïve HBeAg positive
9. Lack of cirrhosis or advanced liver disease as documented by the following:
 - Liver biopsy results of METAVIR F0-F2 (absence of bridging fibrosis or cirrhosis) within 1 year of Screening

OR

 - Fasting FibroScan ≤8 kPa within 3 months of Screening (including Screening visit) or other Sponsor-approved hepatic imaging study (hepatic magnetic resonance elastography [MRE]) within 6 months of Screening indicating lack of cirrhosis or advanced liver disease (F0-F2 or equivalent)

Subjects with a fasting FibroScan >8 kPa and ≤10 kPa are excluded from study participation unless a liver biopsy within the 1 year before Day 1 confirms the absence of bridging fibrosis and cirrhosis. Subjects with a FibroScan >10 kPa are excluded from study participation

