2.2. Final Analysis

As of 01 September 2021, the study is early terminated. The final analysis to support a 'Synoptic Clinical Study Report' will be performed after all subjects have discontinued or completed the 12-week follow-up visits, outstanding data queries have been resolved or adjudicated as unresolvable, and the data have been cleaned and finalized.

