7.2.1.2. Summaries of Laboratory Abnormalities

A summary (number and percentage of subjects) for treatment-emergent graded laboratory abnormalities will be provided by lab test and treatment group; subjects will be categorized according to the most severe postbaseline abnormality grade for a given laboratory test:

For all summaries of laboratory abnormalities, the denominator is the number of subjects with nonmissing postbaseline values up to 28 days after last dose date of ABI-H2158/PBO.

The maximum postbaseline grade observed up to 28 days after last dose date will be tabulated for each laboratory test, and percentages will be based on the number of subjects with a postbaseline evaluation of the specific laboratory test.

Graded lab abnormalities will be also be summarized for the off-treatment period. Lab abnormalities are included starting from 29 days after the last dose of ABI-H2158/PBO.

A by-subject listing of graded laboratory abnormalities will be provided by subject ID number and visit in chronological order. This listing will include all test results that were collected throughout the study for the lab test of interest, with all applicable severity grades displayed.

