7.2.2.2. ALT Elevation with Declining Hepatic Function

A confirmed ALT elevation with evidence of declining hepatic function is defined as meeting the following criteria at 2 consecutive visits:

- ALT elevation $\geq 2 \times \text{Baseline (Day 1)}$ or nadir and $> 2 \times \text{ULN(Covance)}$ AND
- Direct bilirubin increase to $\geq 2 \times \text{Baseline (Day 1)}$ and $\geq 2 \times \text{ULN(Covance)}$ OR
- Albumin decline $\geq 0.5 \text{ g/dL}$ OR $\text{INR} > 2 \times \text{Baseline (Day 1)}$ OR
- Symptoms of liver inflammation (eg, fatigue, weakness, lack of appetite, nausea, vomiting, jaundice or discolored feces)

The number and subjects meeting the above laboratory criteria will be summarized by treatment group. Clinical signs or symptoms of liver inflammation will not be included in the summary. For individual laboratory tests, subjects will be counted once based on the most severe postbaseline values. For the composite criteria, subjects will be counted once when the criteria are met at the same visit. The denominator is the number of subjects in the Safety Analysis Set who have nonmissing postbaseline values. A listing of subjects who met at least 1 of the above criteria will be provided.

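### AEs and the ALT elevations that ended development are summarised only as subject counts or percentages, with no time-to-onset or interval display, although one calendar stop cut short a planned 72 weeks of treatment

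*Combined protocol and SAP*

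**What the plan says.** Safety is a primary objective and a primary endpoint (protocol 3.1.1 and 3.2.1). SAP section 1 records that development was discontinued on 01 September 2021 after ALT elevations consistent with drug-induced liver injury, and SAP 2.2 states: "As of 01 September 2021, the study is early terminated". Planned treatment was 72 weeks (SAP 4.2.1).

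The safety summaries count people:

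- **AEs (SAP 7.1.6):** the "number and percentage of subjects who experienced at least 1 TEAE in the categories described below will be provided by treatment group". An AE is treatment-emergent if it starts "no later than 28 days after permanent discontinuation of ABI-H2158/PBO" (SAP 7.1.5.1).
- **Graded laboratory abnormalities (SAP 7.2.1.2):** "the denominator is the number of subjects with nonmissing postbaseline values up to 28 days after last dose date of ABI-H2158/PBO".
- **ALT elevation (SAP 7.2.2.2):** "The number and subjects meeting the above laboratory criteria will be summarized by treatment group". For single tests, "subjects will be counted once based on the most severe postbaseline values". "The denominator is the number of subjects in the Safety Analysis Set who have nonmissing postbaseline values".

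Exposure is tabulated separately in SAP 4.2.1 and is not linked to events. On cohorts, the protocol synopsis says: "All safety, antiviral activity and PK endpoints will be summarized using descriptive statistics by dose groups within cohorts". SAP section 7 refers only to treatment group, whereas SAP section 6 explicitly separates the cohorts for efficacy.

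**The concern.** A percentage over everyone dosed treats a subject stopped after a few weeks as observed for as long as one treated for a year. When a single calendar date ends treatment for subjects who entered at different times, that percentage mixes risks over unequal periods. It answers no fixed-time question, such as the risk of an ALT elevation by Week 24, and it hides whether onset is early or accumulates with exposure. For a hepatic signal that ended a programme, timing and absolute risk are what a reader most needs from the report.

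The second issue is precision. The planned placebo arm is 10 per cohort. If the protocol's within-cohort rule is the only display, a contrast against 10 subjects says little. Both cohorts have the same ABI-H2158 dose, the same ETV background and the same 3:1 allocation, so a stratified pooled estimate is available.

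**Working it through.** **Figures in the plan.** The sample size has no statistical basis (SAP 1.3), so only the allocation can be reproduced: 40 × 3/4 = 30 and 40 × 1/4 = 10 per cohort, hence 60 v 20 across both. These are planned numbers. All risks, entry patterns and event counts below are assumptions, because the documents give no event rates, onset times or actual exposures.

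**1. Crude percentage against true 24-week risk.** Let time on drug at the stop, t, be uniform on (0, E) weeks, with E = 24, 36 or 48. Events count to t + 4 weeks (the 28-day window) and no later than Week 24. The true 24-week risk is 10%.

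*Constant hazard:* h = −ln(0.9)/24 = 0.00439 per week, continuing through the 28-day window. The crude percentage is the mean of 1 − exp(−h × min(t + 4, 24)). Subjects with t below 20 contribute the integral 20 − (exp(−4h) − exp(−24h))/h = 20 − (0.98259 − 0.9)/0.00439 = 1.186; the rest contribute 0.1 × (E − 20).

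- E = 24: (1.186 + 0.4)/24 = 6.6%
- E = 36: (1.186 + 1.6)/36 = 7.7%
- E = 48: (1.186 + 2.8)/48 = 8.3%

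*Onsets even over the first 16 weeks:* the crude percentage is the mean of 10% × min((t + 4)/16, 1). For t from 0 to 12 the factor averages (4 + 16)/(2 × 16) = 0.625, contributing 12 × 0.625 = 7.5; beyond that it is 1.

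- E = 24: 10% × (7.5 + 12)/24 = 8.1%
- E = 36: 10% × (7.5 + 24)/36 = 8.8%
- E = 48: 10% × (7.5 + 36)/48 = 9.1%

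The shortfall is 1.7 to 3.4 points under a constant hazard and 0.9 to 1.9 points with early onset. SAP 7.2.2.2 states no end to the postbaseline period for its ALT criteria, so applying the 28-day window there is a further assumption.

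**2. Between-arm contrast, both arms truncated alike.** Assume 72-week risks R of 20% v 5%, and take the mean of 1 − (1 − R)^(t/72), without the 28-day tail, for t uniform over 0–72, 12–48 or 4–36 weeks. The risk ratio moves from 4.0 to 4.1, 4.2 or 4.2. The risk difference falls from 15.0 points to 7.9, 6.7 or 4.6.

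**3. Unequal exposure.** Protocol 9.4 stops treatment after a confirmed ALT elevation with declining hepatic function, so active exposure could be shorter. With the same risks and 36 weeks in both arms, the percentages are 1 − 0.8^(36/72) = 10.6% and 1 − 0.95^(36/72) = 2.5%, ratio 4.2. With 30 or 24 weeks on active, the active percentage is 8.9% or 7.2% and the ratio 3.5 or 2.8.

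**4. Precision by cohort and pooled.**

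| Assumed count | One cohort | Pooled |
|---|---|---|
| Placebo, no events: exact upper limit, 1 − 0.025^(1/n) | 0/10: 30.8% | 0/20: 16.8% |
| Active, no events: exact upper limit | 0/30: 11.6% | 0/60: 6.0% |
| Active at 10%: exact 95% CI | 3/30: 2.1% to 26.5% | 6/60: 3.8% to 20.5% |
| Difference of 10 points: Newcombe 95% CI | 3/30 v 0/10: −18.5 to 25.6 | 6/60 v 0/20: −7.0 to 20.1 |

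**The case against.** A reader might infer that hepatic risk is understated as a matter of fact. The documents do not support that. A crude percentage is a valid incidence over the exposure observed; it falls short only of a risk at a longer fixed time, by an amount that depends on onset timing, which is not reported. With early onset the shortfall is small, and truncation common to both arms leaves the risk ratio almost unchanged.

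A reader might also infer that safety will certainly be reported only as 30 v 10. That wording is in the protocol synopsis. Protocol 10.4.4 and SAP section 7 refer to treatment group, so pooled tables remain an open reading, and the loss of precision is conditional on by-cohort tables being the sole display.

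Nor do the exposure bands in SAP 4.2.1 show that exposures differed; they are reporting categories. Unequal exposure is an inference from a single stop date and staggered entry.

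It is fair, too, that this is a descriptive Phase 2a study reduced to a synoptic report without formal testing. Exposure is tabulated, off-treatment events from day 29 are summarised, and listings cover all AEs, graded laboratory results and subjects meeting an ALT criterion. Rates and onset times could be derived later. What stands is that no planned summary shows timing or uncertainty for the events that ended development, and a later derivation would be post hoc. Intervals and Kaplan-Meier estimates are estimation, not testing, and SAP 6.1.2 already gives 95% CIs for HBV DNA.

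**Conclusion.** The point holds as an omission worth repairing, not as a demonstrated bias. The SAP gives counts and percentages over persons for AEs, graded laboratory abnormalities and ALT elevation, and specifies neither onset timing nor an interval. Under the stated assumptions, a true 24-week risk of 10% would appear as 6.6% to 8.3% with a constant hazard or 8.1% to 9.1% with early onset; which case applies cannot be read from the planned tables. Absolute risks and risk differences are the quantities affected. The ratio is largely preserved under equal truncation and moves towards no effect only if active subjects were exposed for less time. The SAP should also say whether safety is pooled, by cohort or both.

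**What to change.** In SAP 7.2.2, and for hepatic AEs in SAP 7.1.6, add:

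1. A Kaplan-Meier cumulative incidence, by treatment group, of time from first dose to first ALT elevation at each level. Censor at the earlier of last assessment and last ABI-H2158/PBO dose + 28 days. Show numbers at risk at Weeks 12, 24 and 48.
2. A pooled summary (60 v 20 as planned) with exact 95% CIs per arm and a cohort-stratified risk difference with 95% CI, alongside by-cohort tables. State explicitly that both displays are produced.
3. Optionally, events per 100 subject-years, as supportive only, because a single rate assumes a constant hazard.

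The cost is SAP wording and two or three extra outputs from dose, onset and laboratory dates already collected. Kaplan-Meier estimation assumes that censoring is unrelated to risk, which is plausible for a calendar stop but less so for individual discontinuations. Pooling mixes HBeAg-positive and HBeAg-negative subjects, which is why the by-cohort display stays.
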